### **Subjects selection criteria**

Adult patients scheduled for thoracoscopic surgery or thoracotomy requiring lung isolation in which both an EZ-blocker or double lumen tube would be considered an appropriate choice for lung isolation will be recruited.

- Inclusion Criteria**

Patients greater than 18 years of age scheduled for thoracoscopic surgery or thoracotomy requiring lung isolation

Patient presenting as an outpatient for elective thoracic surgery

Inpatients scheduled for thoracic surgery.

- **Exclusion Criteria**

History of difficult airway/intubation  
Patients suspected to have a difficult airway.  
Morbid obesity BMI >39  
Pregnancy  
Emergency status of surgery  
Thoracic surgery requiring a right sided double lumen tube

- **Sample Size**

Assuming a power of 80% and a type 1 error of 5% and a rate of repositioning in the DLT group to be approximately 0.3 repositioning/hour from our experience and a projected rate of repositionings using an EZ-blocker of 0.5 with a standard deviation of 0.3 we estimate a sample size of 36 patients in each arm to demonstrate non-equivalence and so we anticipate enrolling 40 patients in each device in both the left and right sided arm bringing our total enrollment to 160 patients. This is not a multisite study.

### **Interventions and Interactions**

Interventions and interactions for the patient should be fairly reasonable. The largest overall commitment of time from the patient will be in the PAC at the time of recruitment or in their room as an inpatient. One of the PAC attendings, or investigators, or study personnel will interview the patient explain the study and attempt to recruit the patient if they are eligible. The study participant will have their questions answered and will be consented.

On the day of surgery, the patient will be identified in the holding area and a study representative will make sure that he or she has not changed their mind about participation and will answer any questions the study subject may have thought of since the interview in PAC. If the patient is still in agreement to participate in the study they will be taken to the OR and care will proceed as it would otherwise with the induction of general anesthesia and placement of the EZ-blocker or DLT per the protocol depending on which group the patient has been randomized to. In some cases, in which the patient is an inpatient or does not go to the PAC a member of the study team may approach them to participate either the day before or on the day of surgery. After the surgery, a study representative will contact the patient to evaluate for any postoperative issues such as a sore throat or increase hoarseness on post-operative days 1 and 2. This will be the last interaction of the patient with the study.

	Patient identified in PAC.	Patient approached in PAC and questions answered about. Patient to sign consent for study participation here.	Confirmation and randomization on day of surgery	Bronchial Blocker placed intraluminally or extraluminally. Data collected about placement	Patient will undergo surgery. Intra-operative events related to blocker position will be recorded	At the end of surgery BB or DLT will be removed, and the patient will extubated, and patient taken to PACU or ICU	Patient interviewed on post-op days 1 and 2 to evaluate sore throat.
Time required of Patient	0 min	20 min	5 min	10 min	Depends on surgical duration.		5-10 min

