The surgeon will be blinded to technique and queried as to the quality of isolation upon entry into the chest and this will be recorded. This will be queried every 60 minutes for the duration of the procedure.

We will record any episodes of loss of isolation and details of repositioning including times and the issue of malposition i.e. the blocker or DLT slipped out or slipped in too far. We will record any episodes of ongoing desaturation which require deflation of the EZ-blocker cuff and/or ventilation of both lungs with a DLT.

We will record the point at which the surgeon the end of OLV. The patient will be extubated according to normal clinical practices and will be taken to the post anesthesia care unit. The Ez-blocker will be removed simultaneously with the ETT. In patients in the EZ-blocker group that remains intubated post procedure the EZ-blocker will be removed prior to going to the ICU. In the DLT group the DLT will be exchanged according to routine clinical practice to a single lumen ETT.

The patient will be contacted on post-operative days 1 and 2 to assessed for hoarseness and sore throat via a VAS scale from 0-100: 0=No sore throat and 100=the worst sore throat imaginable. We will also record any significant morbidity or mortality events such as prolonged mechanical ventilation or cardiac arrest or stroke that may occur within the first 2 post-operative days.

In patients where isolation is troublesome requiring multiple repositioning we will evaluate their preoperative CT scan to determine if there are any anatomical findings on CT which maybe predictive of failure. We will compare these to an equivalent number of control patients from this study population in which isolation was successful. We will attempt to match these patients for size and diagnosis.

The study will be performed at Wake Forest Baptist Medical Center a tertiary academic medical center.

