## Appendix 1 Data Sheet

### Data Form for EZ-bronchial Blocker vs. Double Lumen Study

Patient Sticker

ASA:

Weight:      Height:      BMI:

Gender:

Diagnosis:

Laterality:      RIGHT      LEFT

EZ-Blocker      DOUBLE LUMEN

Induction Drug Doses:

Propofol \_\_\_\_\_      Fentanyl \_\_\_\_\_      Rocuronium(0.8mg/kg) \_\_\_\_\_  
Etomidate \_\_\_\_\_

Ventilate/Wait 3 minutes at least.

Begin Blocker or Double Lumen with DL. START TIMING:

Time for placement of EZ-blocker or DLT: \_\_\_\_\_

Number of EZ-blocker or DLT Replacements During Procedure: \_\_\_\_\_

Quality of Isolation: 1- Excellent      2 – Fair      3 - Poor

Time 1 \_\_\_\_\_      Quality of Isolation T1 \_\_\_\_\_

Time 60 min      Quality of Isolation 60 \_\_\_\_\_

Time 120 min      Quality of Isolation 120 \_\_\_\_\_

Time 180 min      Quality of Isolation 180 \_\_\_\_\_

Time 240 min      Quality of Isolation 240 \_\_\_\_\_

Time 300 min      Quality of Isolation 300 \_\_\_\_\_

(Excellent=complete collapse with perfect surgical exposure; Fair=total collapse but the lung has residual air; Poor=no collapse, or partial collapse with interference in surgical exposure)

Incision Time: \_\_\_\_\_      Closure Time: \_\_\_\_\_      Time of OLV \_\_\_\_\_

Sore Throat Post procedure:  
VAS score from page 3

Day 1 \_\_\_\_\_

Day 2 \_\_\_\_\_

Additional Comments/Adverse Events/Other significant intra-operative events

Blocker or Double Lumen Replacement

Replacement Event:	Time	Brief Description of event including duration of replacement event
		Too Deep Too Proximal Other

## Day 1

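### Nothing in the plan keeps patients or the interviewer unaware of the device when sore throat and hoarseness are self-reported on days 1 and 2, which leaves an avoidable risk of reporting bias in secondary outcomes

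*Combined protocol and SAP*

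**What the plan says.** All references are to the combined protocol and SAP.

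- **Blinding.** The Design section states: "The surgeon will be blinded to technique and queried as to the quality of isolation upon entry into the chest and this will be recorded". No other blinding is described anywhere.
- **Who asks about symptoms.** Of the day 1 and 2 contacts, Interventions and Interactions states: "After the surgery, a study representative will contact the patient to evaluate for any postoperative issues such as a sore throat or increase hoarseness". It does not say whether this person took part in the operation or knows the device.
- **Instrument.** Under Design, patients are contacted "to assessed for hoarseness and sore throat via a VAS scale from 0-100: 0=No sore throat and 100=the worst sore throat imaginable". Both anchors describe sore throat only.
- **Form.** The data sheet in Appendix 1 is titled "Data Form for EZ-bronchial Blocker vs. Double Lumen Study". It has a field to mark the device, "EZ-Blocker DOUBLE LUMEN", and a log of replacement events. Under "Sore Throat Post procedure" it has Day 1 and Day 2 lines to be filled with the "VAS score from page 3". The Day 1 and Day 2 sore throat scales follow in the same appendix. There is no line for hoarseness.
- **Role of these outcomes.** Sore throat and hoarseness come under the additional objective, and their incidence is listed under Outcome Measure(s). They do not enter the sample size.

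**The concern.** Sore throat on a 0-100 scale and self-reported hoarseness are subjective, so the answer can shift with what the patient, or the person asking, believes about the device. The likely direction is known in advance. The Background section reports fewer airway injuries with blockers than with double lumen tubes and makes tube morbidity the reason for the trial. Patients have the study explained to them at consent, and staff know its rationale.

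The plan protects the other subjective rating, the surgeon's, but not this one. What is at stake is the patient-centred part of the comparison: an apparent advantage of the EZ-blocker on throat symptoms could reflect expectation rather than injury. The t-tests and chi-square tests in the Analytical Plan cannot separate the two once the data are collected.

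**Working it through.** **1. The plan's own figure.** The only computed figure is the sample size for the repositioning rate: 0.3 against 0.5 per hour, SD 0.3, power 80%, type 1 error 5%. With n = 2(z₀.₉₇₅ + z₀.₈₀)² × SD² / difference², this is 2 × (1.960 + 0.842)² × 0.3² / 0.2² = 35.3, which rounds up to the stated 36 per arm. The figure reproduces, and the present point does not alter it.

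**2. What the text establishes, item by item.**

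| Question | What the documents show |
|---|---|
| Is the surgeon blinded? | Yes, stated in Design |
| Is the interviewer blinded, or separate from the operating-room team? | Not stated |
| Is the patient told the device, or is it withheld? | Neither is stated |
| Is the sore throat VAS part of the form that records the device? | Yes; it is on a later page and the score is copied back to the data sheet |
| Does the interviewer have the device page in view? | Not stated |
| Is hoarseness on the form? | No |
| Could patients remain unaware? | In principle yes: randomization is on the day of surgery, the device is placed after induction of general anesthesia, and it is normally removed or exchanged at the end of surgery |

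**3. Illustration of sensitivity.** The documents give no SD for the VAS, so the bias b is expressed in SD units. Both the bias and the SD are assumptions. Suppose there is no true difference between devices and reporting alone shifts one group's mean by b. With n per device, the standardized standard error is √(2/n), and

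false-positive rate = 1 − Φ(1.960 − b/√(2/n)) + Φ(−1.960 − b/√(2/n)).

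The sizes come from the Sample Size section: 40 per device per side, so 80 per device over both sides.

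- n = 80: √(2/80) = 0.158; for b = 0.2 the shift is 0.2/0.158 = 1.265; the rate is 1 − Φ(0.695) + Φ(−3.225) = 24.4%.
- n = 40: √(2/40) = 0.224; for b = 0.2 the shift is 0.2/0.224 = 0.894; the rate is 1 − Φ(1.066) + Φ(−2.854) = 14.5%.

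| Assumed bias | 80 per device | 40 per device, one side |
|---|---|---|
| 0 | 5.0% | 5.0% |
| 0.1 SD | 9.7% | 7.3% |
| 0.2 SD | 24.4% | 14.5% |
| 0.3 SD | 47.5% | 26.9% |

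In VAS points, 0.2 SD is 5 points if the SD is 25. The noncentral t gives 24.2% (80 per device) and 14.3% (40 per device) for that case. With 80 per device and SDs of 20, 25 and 30, a 5-point bias gives 34.9%, 24.2% and 18.2%, and a 3-point bias gives 15.6%, 11.7% and 9.6%.

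**The case against.** The strongest reply is that this is an argument from silence. No text says that patients learn their device, and the consent text was not available for this review. Nor does any text say that the interviewer carries the data sheet. Because the VAS is on its own page, the layout fits an interviewer who uses that page alone. A reader might infer that the form as built unblinds the interviewer, or that patients and interviewers know the device. The documents support neither reading, and this part of the objection stands.

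It also stands that the form argument covers sore throat only, because the form has no hoarseness item. That missing item is a separate gap.

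On size, the bias is chosen rather than observed, and the false-positive rate depends heavily on the choice. The calculation concerns mean VAS, whereas Outcome Measure(s) lists incidence, for which the Analytical Plan offers chi-square tests; the figures do not carry over to that analysis. The trial is also sized within side, where the inflation is smaller. Finally, these are secondary outcomes.

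What the objection does not remove is the absence of any safeguard. The plan blinds the surgeon, leaves the symptom interview open, and ties the sore throat scale to the form that records the device. An interviewer who followed the plan to the letter could know the allocation, and simple measures would prevent that.

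**Conclusion.** The point holds as an avoidable risk of reporting bias in day 1 and 2 sore throat and hoarseness, not as a demonstrated unblinding. Blinding is specified only for the surgeon's isolation rating; nothing protects the self-reported symptoms, and the sore throat VAS shares a form with the device field.

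The about 24% (80 per device) and about 14% (40 per device within one side) assume a bias of 0.2 SD, no true difference and a two-sided 5% test on mean VAS. They show how sensitive the comparison would be and do not estimate the bias that will occur. The repositioning comparison and its sample size are unaffected. This is a worthwhile improvement rather than a flaw that threatens the trial's main result.

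**What to change.** 1. Add a sentence to Design stating that patients are not told which device was used until after the day-2 contact, unless disclosure is clinically needed.
2. Move the day 1 and 2 items to a detached sheet carrying only the study identifier, with no device field or replacement log. Give hoarseness its own item there, since the present form has none.
3. Where existing staffing allows, have the contact made by a team member who was not in that patient's operating room and does not have the device page. The documents give no staffing figures, so this should not be an absolute requirement.

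The cost is one split form page, the added protocol text and minor scheduling among the team. Patients who ask would normally wait until after day 2 to learn their device. Sample size and the number of patient contacts do not change.

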## **Methods and Measures**

### **Design**

Once the patient is recruited preoperatively in the PAC or within the hospital as an inpatient, this information will be relayed to the study investigators. On the day of surgery, the patient will then be randomized using a random number generator and opaque envelope method for group allocation to either extra-luminal placement of an EZ blocker bronchial blocker or left side double lumen tube. We will recruit at least 80 patients with right sided procedures: 40 EZ-Blocker and 40 left sided DLT. We will also recruit at least 80 patients with left sided procedures: 40 EZ-Blocker and 40 left sided DLT.

We will record age, height, weight, gender, ASA status, type of surgery, side of surgery, duration of one lung ventilation, duration of surgery, and duration of anesthesia.

An IV will be placed in the patient prior to going to the OR. Once in the OR the patient will have routine monitors placed. The patient will be pre-oxygenated with 100% O2 for 2 minutes and induced.. The patient will then be hand ventilated with 100% oxygen for 3 minutes to ensure relaxation. Patients will undergo direct laryngoscopy and according to group assignment will have either an extraluminal EZ-blocker placed or an appropriately sized left sided double lumen placed under the supervision of an attending experienced in thoracic anesthesia and one lung ventilation.

We will confirm endotracheal placement of the ETT or left sided DLT via auscultation and ETCO2. The ETT or DLT will be secured at an appropriated depth. The fiberscope will then be advanced into the lumen of the ETT or DLT to further adjust and confirm placement of the EZ-blocker or DLT. Time for initial bronchial blocker placement or DLT placement will be recorded from the point of the DL to removal of the fiberscope after visualization of the BB with the cuff inflated in the correct position or the DLT with the bronchial cuff inflated.

Other intravascular lines such as a radial arterial line and additional peripheral IV may be placed at the discretion of the attending anesthesiologist.

Once in the final position prior to prepping and draping the blocker or DLT in all groups will be checked to make sure it is still correctly placed with a FOB. The patient will be prepped and draped.

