### **Outcome Measure(s)**

We will measure the number of DLT or BB replacements, time of placement, quality of isolation at 1-hour intervals during the operation, incidence of sore throat and/or hoarseness postoperatively.

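### Postoperative sore throat and hoarseness incidence has no preoperative reference, so existing symptoms that persist would inflate both rates and shrink the yes/no device difference

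*Combined protocol and SAP*

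**What the plan says.** The Outcome Measure(s) section lists "incidence of sore throat and/or hoarseness postoperatively". Under Design, the assessment is: "The patient will be contacted on post-operative days 1 and 2 to assessed for hoarseness and sore throat via a VAS scale from 0-100". Interventions and Interactions describes the same contact as one to "evaluate for any postoperative issues such as a sore throat or increase hoarseness on post-operative days 1 and 2". Incidence and increase both refer to a state before surgery.

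No such state is recorded:
- **Baseline list (Design).** "We will record age, height, weight, gender, ASA status, type of surgery, side of surgery", followed by durations of one-lung ventilation, surgery and anaesthesia. It has no throat or voice item.
- **Data form (Appendix 1).** The throat entry is headed "Sore Throat Post procedure" and has sore throat VAS scores for Day 1 and Day 2 only. It has no preoperative score and no hoarseness field at any time.
- **Eligibility (Subjects selection criteria).** The six exclusions begin with "History of difficult airway/intubation". The others are suspected difficult airway, BMI above 39, pregnancy, emergency surgery and need for a right-sided tube. None concerns existing throat or voice symptoms.
- **Analytical Plan.** It names chi-square tests for proportions and t-tests or ANOVA for continuous variables, with no baseline adjustment.

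A suitable contact already exists. On the day of surgery "a study representative will make sure that he or she has not changed their mind about participation", and the visit table allots five minutes to this confirmation and randomisation.

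**The concern.** A patient who arrives with a sore throat and still has it on Day 1 looks, in these data, the same as a patient whose sore throat began with the device. If presence of the symptom is counted as incidence, such patients add events unrelated to the device to both arms. Both rates are then overstated and the contrast between devices is understated.

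The Background gives possible airway injury from double lumen tubes as a reason for further study. Sore throat and hoarseness are the only airway-morbidity measures named under Outcome Measure(s). They belong to the additional objective, and the sample size does not rest on them. Even so, a diluted comparison could be read as evidence that the devices differ little in this respect. The missing value cannot be measured once the airway has been instrumented.

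**Working it through.** **1. The plan's own figure.** Sample Size assumes 0.3 versus 0.5 repositionings per hour, SD 0.3, 80% power and 5% type 1 error. Taken as two-sided: n = 2 × (1.960 + 0.842)² × 0.3² / 0.2² = 35.3, rounded up to 36 per arm. This reproduces the stated 36. It concerns repositioning, and nothing below changes it. The documents give no rate or power for sore throat or hoarseness.

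**2. Inputs for the symptom outcome.** From the documents: 40 patients per device on each side, so 80 per device overall. Assumed: new-onset rates p of 20% (EZ-blocker) and 40% (double lumen tube), two-sided 5% testing, and a share b of patients who have the symptom before surgery and still report it afterwards.

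**3. Effect on the rates.** Observed rate q = b + (1 − b)p in each arm. Subtracting the arms, the observed difference is (1 − b) times the true difference. At b = 10%:
- EZ-blocker: 0.10 + 0.90 × 0.20 = 0.28
- Double lumen tube: 0.10 + 0.90 × 0.40 = 0.46
- Difference 0.18; risk ratio 0.46 / 0.28 = 1.64

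**4. Effect on power.** Power = Φ{[d − 1.96 √(2q̄(1 − q̄)/n)] / √([q₁(1 − q₁) + q₂(1 − q₂)]/n)}, where d is the observed difference and q̄ the mean of the two rates. At b = 10% and n = 80, q̄ = 0.37, the two standard errors are 0.0763 and 0.0750, and (0.18 − 1.96 × 0.0763)/0.0750 ≈ 0.41, so power is about 66%.

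The last column applies the true rates to the symptom-free patients only, n = 80(1 − b) per device.

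| b | EZ | DLT | Difference (points) | Risk ratio | Power, no baseline | Power, symptom-free only |
|---|---|---|---|---|---|---|
| 0 | 20.0% | 40.0% | 20.0 | 2.00 | 79% | 79% |
| 2% | 21.6% | 41.2% | 19.6 | 1.91 | 77% | 79% |
| 5% | 24.0% | 43.0% | 19.0 | 1.79 | 73% | 77% |
| 10% | 28.0% | 46.0% | 18.0 | 1.64 | 66% | 75% |
| 20% | 36.0% | 52.0% | 16.0 | 1.44 | 53% | 70% |

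**5. Other assumed rates.** At b of 5%, 10% and 20%, power without a baseline falls from 74% to 68%, 63% and 53% for 30% versus 50%. It falls from 62% to 53%, 46% and 35% for 15% versus 30%.

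**6. Mean VAS.** If an existing score adds to whatever the device causes, it adds the same expected amount in both randomised arms and cancels from the difference in means. What remains is extra variance. The dilution in step 3 therefore belongs to the yes/no outcome only.

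**The case against.** The strongest reply is that the size is entirely assumed. The documents give no prevalence of existing symptoms, and at b of 2% to 5% the difference moves by one point or less. The formula also counts only symptoms that persist to the postoperative contact. This stands: the direction follows from algebra, but the amount is unknown. Without a preoperative item the trial could not show which case applies.

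A second reply is that an interviewer can ask whether hoarseness is worse than before surgery. This is a partial remedy by recall, for hoarseness only. The sore throat VAS runs from none to worst imaginable, and neither Design nor Outcome Measure(s) carries the comparative wording.

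A reader might infer more than the documents support:
- *That the comparison is biased toward one device.* Randomisation balances existing symptoms in expectation. A chance imbalance could, however, be neither seen nor adjusted for.
- *That all throat comparisons are diluted.* Mean VAS is not, as step 6 shows.
- *That the form scores an already hoarse patient as a device injury.* It has no hoarseness field, so it scores no one for hoarseness. That is a gap of its own.
- *That inpatients bring recent intubation or bronchoscopy.* The plan says only "Inpatients scheduled for thoracic surgery"; their airway history is conjecture.
- *That the Background prefers the blocker on airway grounds.* It calls for further exploration and states no preference.
- *That 40 per device is the relevant number.* No side-specific symptom analysis is planned; the overall comparison has 80 per device.

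**Conclusion.** The point holds as a limited, inexpensive improvement to a secondary-type outcome. Incidence and increase are named without any recorded preoperative reference, and patients with existing symptoms may enter. For the yes/no incidence, persisting symptoms inflate both rates and multiply the risk difference by (1 − b). Under the assumed 20% versus 40%, the consequence runs from negligible at b = 2% (two points of power) to substantial at b = 20% (26 points of power). Those figures rest on assumed rates, full persistence of the existing symptoms counted in b, and a two-sided 5% test. Eligibility itself is not the defect; the missing baseline item is.

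**What to change.** - At the existing day-of-surgery confirmation, before the allocation envelope is opened, record the 0-100 sore throat score and hoarseness (yes/no).
- Add to the data form a preoperative sore throat score, and a hoarseness item for the preoperative contact, Day 1 and Day 2.
- Define incidence, for each symptom, as new onset among patients free of that symptom at baseline, with the same rule for presence at all times. Because the subset is fixed before allocation is known, the comparison remains randomised.
- Compare Day 1 and Day 2 VAS with adjustment for the preoperative score (ANCOVA), keeping all patients.
- Leave eligibility unchanged; every patient still counts for the positional-stability outcome.

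The cost is about one minute of data collection within a five-minute contact, and an incidence denominator smaller by the baseline prevalence, up to 20% in the assumed range. With full persistence this still leaves more power than having no baseline: 70% against 53% at b = 20%. That gain is not guaranteed. If 20% had symptoms but only a quarter of them persisted, the contaminating share would be 0.20 × 0.25 = 5%. Power without a baseline would then be 73%, slightly above the 70% from restriction. The restricted analysis would still be the one that measures new onset.
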